## **3.3 Recombinant AAV Vectors**

Recombinant AAV (rAAV) vectors are composed of a transgene expression cassette between inverted terminal repeats (ITRs), which guide packaging of vector DNA into AAV capsids. rAAV vectors are non-toxic, highly efficient at transducing a wide variety of non-dividing cell types, and persist for long periods potentially leading to long-term expression of the transgene ([Carter PJ, Samulski RJ 2000](#)).

## **3.4 Human Clinical Experience with AAV2 Vectors**

AAV2 is currently being used as the vector of choice in multiple clinical studies around the world setting a precedent as a safe delivery system for gene therapy. Specifically, AAV2 has been used as a vector in clinical studies within the United States since 2004. To date there are no approved products utilizing AAV2 but there are a number of clinical studies that either have been completed or are ongoing worldwide, some of which are in the area of ophthalmology, including indications like neovascular age-related macular degeneration, Leber Congenital Amaurosis (LCA), and choroideremia.

## **3.5 RST-001**

RST-001 (AGN-151597) is a gene therapy product based on the light-gated ion channel, channelrhodopsin-2 (ChR2). RST-001 comprises a non-replicating recombinant

Adeno-Associated Virus serotype [REDACTED] containing the [REDACTED]  
[REDACTED]  
[REDACTED]  
[REDACTED]. RST-001 is manufactured in sterile conditions according to Good Manufacturing Practice (GMP) requirements, which includes screening and elimination of microbes.

### 3.6 Nonclinical Studies with RST-001

#### 3.6.1 Pharmacology Studies

Two studies were conducted in mice, collectively covering a 10-fold range of dose exposure from the lowest ([REDACTED] vg/eye) to the highest dose ([REDACTED] vg/eye). The objective of these studies was to test the behavioral efficacy of a single-1  $\mu$ L intravitreal injection in both eyes of RST-001 (dosing solutions (vg/mL): [REDACTED] (Low); [REDACTED] (Mid); [REDACTED] (High)) on visual function in C3H/HeJ-Pde6brd1 mice ([REDACTED] hereafter “C3H”). These mice are homozygous for the retinal degeneration 1 mutation (*Pde6brd1*), which causes blindness by weaning age. The sighted control mice were C3Sn.BLiA-Pde6b+/DnJ ([REDACTED] hereafter “C3Sn”). Behavioral assessments were done prior to AAV2-ChR2 (RST-001) (when mice are ~ 8 weeks old; hereafter “Baseline”), again starting at P120 (hereafter “Test 1”), and finally at 6 months post injection (hereafter “Test 2”). Viral injections were done around 9 weeks old.

There were no injection-related complications and no animals died during the perioperative time period. At the two-month time point, there was evidence of improved visual function in rd1 mice treated with RST-001 at all doses ([REDACTED] vg/eye, [REDACTED] vg/eye, and [REDACTED] vg/eye) evaluated as compared with vehicle injected mice, based upon optokinetic responses. The highest dose ([REDACTED] vg/eye) also showed efficacy for visual placement responses. These effects were investigated in the high dose at 6 months post injection, but were not reproduced. However, electrophysiological measures appear to have verified ChR2-driven light responses at the ganglion cell layer 10 months post injection.

Non-GLP safety observations were also conducted in conjunction with this pharmacology study. RST-001 produced no signs of test article related effects on body weights, food consumption, clinical observations or during ophthalmic examinations. There were no gross lesions at terminal necropsy related to the test article treatment. Histological evaluations were conducted for animals in the control and highest dose group. No test item-related microscopic findings were

noted in the tissues examined (brain, epididymis, eye, heart, kidney, liver, lung, mandibular and mesenteric lymph nodes, optic nerve, parotid salivary gland, spleen and testis).

### **3.6.2 Toxicology and Biodistribution Studies**

Two nonclinical GLP toxicology and biodistribution studies have been completed in two species, beagle dogs and mice. The objectives of both studies were to determine the potential ocular toxicity of RST-001 when given by a single intravitreal injection and to evaluate the potential reversibility of any findings within 99 days of treatment.

The following parameters and end points were evaluated: clinical signs, body weights, food consumption, ophthalmology, clinical pathology parameters (hematology, coagulation, clinical chemistry and bone marrow smear evaluation), immunogenicity [REDACTED]  
[REDACTED], gross necropsy findings, organ weights, and histopathologic examinations, and biodistribution.

#### **3.6.2.1 Dog Study**

The dog study was conducted in healthy male and female animals 5-6 months of age. The dog was chosen as the animal model for this study as it is an accepted non-rodent species for preclinical ocular toxicity testing by regulatory agencies. There were 8 dogs per dose group and 4 dose groups. Actual doses verified were vehicle (control); [REDACTED] (Low), [REDACTED] (Mid), and [REDACTED] (High) vg/eye of RST-001. Two dogs/sex/time point were administered, in the right eye, a single- [REDACTED]  $\mu$ L intravitreal injection of vehicle or RST-001. Animals were sacrificed on Day 36 and Day 99.

No noteworthy adverse effects were observed in the body weight, food consumption, clinical pathology or organ weights following administration of RST-001 at any dose level.

RST-001-related findings, consisting of ocular inflammation, were observed beginning at least 5 weeks after administration with an increasing incidence and severity with dose at all dose levels. Ophthalmic findings of anterior uveitis (anterior chamber cells, keratic precipitates and/or cell-like deposits on the corneal endothelium) were observed at Week 5 in 8/8 high dose eyes and 3/8 or 1/8 eyes for the mid and low doses, respectively. During the recovery period, findings generally remained stable or progressed. Findings related to chronic inflammation, including the presence of perivasculär retinal opacities in addition to findings in the anterior chamber, were present at all dose levels at the end of the recovery period. In 2/8 high dose animals, the level of inflammation was greater when compared to other animals and was accompanied by anterior chamber flare, fibrin, corneal edema, pupil incomplete dilation, fundus hazy view, corneal vessels and/or lens opacities. These observations correlated with microscopic

findings. At the high dose, these consisted of minimal to marked mixed cell (lymphocytes, macrophages, and rarely, neutrophils) inflammation of the anterior chamber (iridocorneal angle), iris, ciliary body, vitreous body and/or retina. At the mid and low dose, findings were limited to minimal to mild cell inflammation in the ciliary body, vitreous body and/or iris. There were no signs of overt tissue damage due to direct toxicity of the test item and no cellular or humoral immune response to RST-001 was detected at any dose level.

RST-001 DNA was detected predominantly in the spleen, with lower concentrations below the limit of quantitation (█ copies/µg of tissue) also detected within the mandibular lymph node, liver, lacrimal gland, and optic nerve. Preliminary immunohistochemistry evaluation of the dogs' retina suggests ChR2 protein expression persistent throughout the 99 days of follow up.

In conclusion, administration of RST-001 by a single intravitreal injection at a 10-fold difference in nominal doses resulted in dose-related ocular inflammation, with no noteworthy adverse effects observed in the body weight, food consumption, clinical pathology, cellular immune response or organ weight. There were no signs of overt tissue damage due to direct toxicity of the test item and no cellular immune or humoral response to RST-001 was detected at any dose level. RST-001 had minimum biodistribution systemically and was expressed in the retina.

### 3.6.2.2 Mice Study

The purpose of this study was to evaluate the toxicity of the test article, RST-001, when given as a single 1 µL intravitreal injection in the right eye to C3H/HeJ-Pde6brd1 mice.

Mice historically have been used in safety evaluation studies and this particular strain is a disease model for advanced RP, the indication of RST-001.

There were 64 mice per dose group and 4 dose groups. Actual doses verified were: vehicle (control); █ (Low), █ (Mid), and █ (High) vg/eye of RST-001. After dosing, animals were observed post dose for at least 29 (interim sacrifice) or 89 days (terminal sacrifice). There were 16 animals/sex/group at each terminal sacrifice.

There are no signs of test article related effects on body weights, food consumption, and clinical observations or during ophthalmic examinations through Week 4 of the dosing phase. There were no gross lesions at any of the terminal necropsy intervals that appear to be related to the test article treatment. There were no signs of overt tissue damage due to direct toxicity of the test item and no cellular immune or humoral response to RST-001 was detected at any dose level.

RST-001 was present at the highest level in the right eye and optic nerve of all animals tested. RST-001 was also detected just above the minimum level of detection (█ copies/µg of tissue)

within the hindbrain and spleen. Dose-dependent minimal to moderate ChR2 immunolabeling occurred in the right treated eye of animals given [REDACTED] vg/right eye; minimal ChR2 immunolabeling was also present in the right optic nerve of some animals with ChR2 immunolabeling in the right eye.

In conclusion, administration of RST-001 by a single intravitreal injection at a 10-fold difference in nominal doses resulted in no dose-related effects. RST-001 had minimum biodistribution systemically and was expressed in the retina.

### **3.6.3 Justification for Human Dose**

The doses and injection volume have been calculated by allometric scaling from pre-clinical animal studies. Vitreous humor volume was the scaling factor across species. In general, scaling of the vitreous volume from mice and dogs to humans is 1:100 and 1:2, respectively.

Two nonclinical toxicology studies were conducted in the dog and mouse. The safe intravitreal doses in the dog ranged from [REDACTED] to [REDACTED] vg/eye. For the mouse, the safe intravitreal doses ranged from [REDACTED] to [REDACTED] vg/eye. Two nonclinical pharmacology studies demonstrated efficacy and safety in the mouse at a dose range of [REDACTED] to [REDACTED] vg/eye in a dose range comparable to the toxicology study. Based on these studies, the expected safe dose range in humans is between [REDACTED] and [REDACTED] vg/eye. The dose range in this study ([REDACTED] to [REDACTED] 1 vg/eye of RST-001) is based on the more conservative exposure in the dog, inclusion of potentially efficacious doses, the ability of the manufacturer to concentrate investigational product, and a safe injection volume of 100  $\mu$ L per eye in humans.

## **3.7 RST-001 Study Rationale: Optogenetic Therapy for Advanced Retinitis Pigmentosa**

RST-001 is a gene therapeutic treatment that renders cells in the retina sensitive to light. This light sensitivity is conveyed to the brain and is a photoreceptor substitute in conditions such as advanced RP where the normal light sensitive cells are lost.

The disease of advanced RP results in the irreversible loss of photoreceptors, which are the only cells in the retina that are able to convert the light entering the eye into an electrical signal that can be relayed to the brain and interpreted as vision. Although these cells degenerate, many of the other neuronal cell types that receive input from the photoreceptors persist. In particular, the innermost retinal cells, the retinal ganglion cells (RGCs) survive in significant numbers late into the disease and axons from these cells remain connected directly to the brain.

Direct electrical stimulation of the RGCs using surgically-implanted electronic devices have provided a proof of concept that vision can be mediated through these cells.

RST-001 delivers a gene encoding a photo switch, channelrhodopsin-2, to the RGCs. When expressed, the channelrhodopsin-2 protein can depolarize in response to light thus generating a signal that is transmitted to the brain. The components of RST-001 are shown in detail above.

The study is composed of two phases. An initial dose-escalation study (Phase 1) is proposed whereby three dose levels of RST-001 will be studied in three separate groups of adult patients with advanced disease. Phase 1 is aimed at determining a single dose of the experimental treatment which is safe and well tolerated, to further evaluate in a fourth group of patients. If the Data Safety Monitoring Committee (DSMC) considers the safety and tolerability of RST-001 satisfactory in the first phase, then the study may proceed to Phase 2a. Phase 2a is aimed at obtaining additional safety data at the maximum tolerated dose. An additional objective of Phase 2a is to provide important additional clinical data to guide the design of future efficacy studies.

### **3.7.1        Immunogenicity of RST-001**

Preclinical data indicated that no cellular or humoral immune response to RST-001 was detected at doses up to [REDACTED] and [REDACTED] vg/eye in mice and dogs, respectively. In this study, evidence of an immune response to the product will be carefully assessed by monitoring for systemic measurement of humoral and cellular immunity. Local or systemic immune suppression may be initiated if clinically indicated.

## **3.8        Treatment Administration**

RST-001 will be administered by intravitreal injection as specified in the Study Procedures Manual. The injection volume is 100  $\mu$ L.

Prior to study treatment administration, the study eye of each patient will be prepared using a standard protocol as described in the Study Procedures Manual.

## **3.9        Objectives of the Study**

### **3.9.1        Primary Objective:**

To evaluate the safety of a single intravitreal injection of RST-001.

### **3.9.2        Secondary Objectives:**

1. To establish the maximum tolerated dose of RST-001.
2. To evaluate the preliminary efficacy of RST-001 in patients with advanced RP.

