#### **3.15.1.1 Enrollment Phase 1**

Three groups of patients (A, B, C, each comprising of approximately but no less than three patients) will be enrolled in this study.

Approximately 3 patients in Group A will receive the lowest dose of RST-001 (LOW). The safety and tolerability of RST-001 will be assessed in the first patient for a minimum of one month (to include Month 1 Visit). If the DSMC considers the safety and tolerability of the first patient satisfactory and the enrollment stopping rules have not been met, then the remaining patients in Group A can be enrolled and receive treatment.

If the DSMC considers the safety and tolerability of Group A satisfactory and the enrollment stopping rules have not been met after a minimum assessment of one month (to include Month 1 Visit) from the last treatment group, then approximately 3 patients in Group B may be enrolled and receive a higher dose of RST-001 (MID) following the same guidelines and treatment schedule.

Similarly, if the DSMC considers the safety and tolerability of Group B satisfactory and the enrollment stopping rules have not been met after a minimum assessment of one month (to include Month 1 Visit) from the last treatment group, then approximately 3 patients in Group C may be enrolled and receive the highest dose of RST-001 (HIGH) following the same guidelines and treatment schedule.

[figure not shown]
After completion of the 2-year core study visits, each patient will be enrolled in a long-term follow-up for an additional 3 years to monitor the long-term safety of RST-001.

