### **3.15.1.2 Enrollment Phase 2a**

If the DSMC considers the safety and tolerability satisfactory and the enrollment stopping rules have not been met after a minimum assessment of one month (to include Month 1 Visit) from treatment of the final patient in Groups A, B, or C, then the sponsor may elect to start enrollment in the second cohort of patients. In Phase 2a, up to approximately 12 patients may be enrolled and receive RST-001 at the maximum tolerated dose.

- If the DSMC considers the data from Phase 1, in their opinion, to be indicative of a treatment benefit for visual acuity/function, then approximately 6 patients will be enrolled in Phase 2a and follow the same eligibility criteria as Phase 1.
- If the DSMC considers the data from Phase 1, in their opinion, to **not** be indicative of a treatment benefit, then approximately 12 patients will be enrolled in Phase 2a.
  - 6 patients must have VA of no-better-than hand motion in the study eye.
  - 6 patients must have VA in the study eye to range from no-worse-than count fingers to 20/200 vision.

A schematic providing an overview of the treatment schedule is illustrated in [Figure 1](#), and the dose-escalation cohorts are illustrated in [Table 1](#) below.

**Figure 1** Overview of the Treatment Schedule**Table 1** Dose Escalation

Phase	Group	Number of patients a	Intravitreal Injection	
			Vector concentration	Volume (µL)
1	A	3	LOW	100
	B	3	MID	100
	C	3	HIGH	100
2a		6-12 b	Choice of dose c from groups A, B, or C	100

a Up to approximately 21 patients will be enrolled in this study.b Number of patients is dependent upon whether or not the DSMC determines that, in their opinion, a treatment benefit for visual acuity/function has been observed in Phase 1.c The maximum tolerated dose.

After completion of the 2-year core study visits, each patient will be enrolled in a long-term follow-up for an additional 3 years to monitor the long-term safety of RST-001.

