### **4.4 Dose Rationale**

The highest feasible concentration of RST-001 is constrained by manufacturing capabilities and product stability and has been determined to be approximately [REDACTED] vg/ml. The highest feasible dose is then limited by the volume that can be delivered to the human vitreous. Based upon estimated vitreous volumes and maximum feasible intravitreal dosing, this maximum

concentration was evaluated as the highest dose in our mouse pharmacology study (dose volume of 1  $\mu$ l) and mouse (1  $\mu$ l) and dog (█  $\mu$ l) toxicology and biodistribution studies. This dose was demonstrated to be efficacious and no dose-limiting toxicity was observed, respectively. Since the beagle dog vitreous has about half the vitreous volume of the human eye, the HIGH dose for the human study has been determined to be █ vg/eye given as a single 100  $\mu$ l intravitreal injection. In order to be safe and conservative but also balanced with the potential for delivering an active dose, Allergan proposes that the LOW initial starting dose for the first-in-human study be █ of this dose, █ vg/eye. The MID dose will be █ of the HIGH dose, █ vg/eye.

Dose escalation will proceed according to [Table 1](#), only after review by the DSMC (see [Figure 1](#), above). Three doses have been chosen with the safety as the priority but will provide a good opportunity to observe biological effect.

The rationale for the dosing schedule is once again based primarily on patient safety. Thus, at each dose a single patient will receive treatment followed by an intensive period of observation for any evidence of AEs prior to dosing the remaining two patients in the group. The safety and tolerability and optimal single dose of RST-001 will therefore be established in Phase 1. Phase 2a patients will receive a single intravitreal injection of RST-001 at the maximum dose tolerated by Phase 1 patients.

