## 7.4 Enrollment Stopping Rules

Enrollment will be suspended pending a complete safety review by the sponsor of all patients including causality to determine the appropriateness of continuing dosing in the occurrence of the following events:

1. Any Grade 3 or greater AE related to RST-001 (according to Common Terminology Criteria for Adverse Events v4.03)
2. Occurrence of an intraocular infection related to contaminated RST-001 that required treatment would serve as a stopping rule
3. A safety issue has been identified that compromises the benefit or increases the risk balance

Dose-limiting toxicity (DLT) is defined as any adverse event of Grade 3 or higher that is expected to be related to the study treatment.

Dose escalation will stop if a DLT is observed, including:

4. Severe or persistent ocular inflammation
5. Other significant ocular toxicity (e.g., retinal detachment, evidence of direct toxicity)

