### **11.3.1 Power and Sample Size Considerations**

The sample size for this study was chosen empirically; no formal sample size computations to meet power requirements were made. The sample size of approximately 3 patients for each dose group in Phase 1 are typical for dose escalation studies, an additional up to approximately 12 patients will be enrolled in Phase 2a for further safety and efficacy evaluation.

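### The design can show which of three tested doses had no observed dose-limiting toxicity, but it cannot establish a maximum tolerated dose, and the SAP text plans no count of such toxicities

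*Protocol*

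**What the plan says.** Protocol 3.9.2 lists "To establish the maximum tolerated dose of RST-001" as the first secondary objective, and SAP 5.0 repeats it.

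The design elements behind that objective are:

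- **Groups.** Protocol 3.15.1.1 has groups A, B and C, "each comprising of approximately but no less than three patients". Protocol 11.3.1 calls the size empirical: "no formal sample size computations to meet power requirements were made".
- **DLT.** Protocol 7.4: "Dose-limiting toxicity (DLT) is defined as any adverse event of Grade 3 or higher that is expected to be related to the study treatment". Grading under the stopping rule is by CTCAE v4.03.
- **Escalation.** Protocol 7.4: "Dose escalation will stop if a DLT is observed, including" two ocular examples. Escalation also needs a satisfactory DSMC view "after a minimum assessment of one month (to include Month 1 Visit) from the last treatment group".
- **Top dose.** Protocol 4.4: "The highest feasible concentration of RST-001 is constrained by manufacturing capabilities and product stability". It then adds the volume that the vitreous can take and scaling from the dog eye. It reports no dose-limiting toxicity in the animal toxicology studies.
- **Use of the result.** Protocol 3.15.1.2: "up to approximately 12 patients may be enrolled and receive RST-001 at the maximum tolerated dose". The same label appears in the synopsis, 3.7, Table 1, 4.3, 4.4 (in slightly different words) and SAP 4.0.

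Neither document gives a target DLT rate, a DLT-evaluable set, or a rule for naming the MTD after zero or one DLT. Protocol 11.1 and 11.2 list no DLT or MTD endpoint. The SAP text does not mention DLTs.

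**The concern.** An MTD is a statement about where toxicity becomes unacceptable. To support it, a design must be able to meet unacceptable toxicity and must say how many events, in how many patients, mark the limit. Here the dose range ends where feasibility ends, and each step is judged on about three patients.

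If all three groups pass, HIGH is simply the highest dose tested. If a DLT occurs at MID or HIGH, the dose below has zero DLTs in about three patients, and the dose above may be ruled out by one event.

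What is at stake is the conclusion carried out of the trial. Phase 2a is meant to guide the design of later efficacy studies, and a dose reported as the MTD would carry more certainty than the data hold. The objective also has no planned output, so nothing in the analysis would show a reader how thin the evidence is.

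**Working it through.** **Stated sample size.** 3 × 3 + 12 = 21, which matches the stated total of up to approximately 21. If the DSMC sees a benefit, it is 3 × 3 + 6 = 15. There is no power or precision figure to reproduce.

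**What zero DLTs shows.** For 0 events in n patients, the exact (Clopper-Pearson) two-sided 95% upper limit is 1 − 0.025^(1/n).

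| Evidence at one dose | n | Upper limit |
|---|---|---|
| Phase 1 group | 3 | 70.8% |
| Phase 1 + 6 in Phase 2a | 9 | 33.6% |
| Phase 1 + 12 in Phase 2a | 15 | 21.8% |

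Only the first row is available when the Phase 2a dose is chosen. The other two require pooling across phases, which SAP 11.1 does not plan.

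**How often a dose passes.** The documents give no DLT rate, so the rates below are assumptions. Three patients are treated, with independent outcomes.

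| True DLT rate | No DLT in 3: (1 − p)³ | At least one: 1 − (1 − p)³ |
|---|---|---|
| 5% | 85.7% | 14.3% |
| 10% | 72.9% | 27.1% |
| 20% | 51.2% | 48.8% |
| 30% | 34.3% | 65.7% |
| 40% | 21.6% | 78.4% |

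A dose with a 30% rate passes about one time in three, and a dose with a 10% rate halts escalation about one time in four.

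**If a DLT occurs at the next dose.** One in three has an exact 95% interval of 0.8% to 90.6%, so the bracket from above is also weak.

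**How often no DLT is seen at any dose.** With assumed rates of 5%, 10% and 20% at LOW, MID and HIGH: 0.95³ × 0.90³ × 0.80³ = 0.857 × 0.729 × 0.512 = 32.0%. With 2%, 5% and 10%: 0.98³ × 0.95³ × 0.90³ = 58.8%. In those trials HIGH would carry the MTD label although no dose had shown a DLT.

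**Whether the SAP tables give a DLT count.**

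- Protocol 7.4 defines a DLT by Grade 3 or higher plus relatedness, and grades by CTCAE.
- Protocol 8.1.3 records intensity as mild, moderate or severe.
- SAP 11.1 tabulates treatment-related events by that severity, and SAP 15.6 imputes missing values on the same scale.

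Severe under 8.1.3 is not defined as Grade 3 or higher, so the planned tables do not yield the DLT count.

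**The case against.** The strongest reply is that the term already has a working meaning. Protocol 4.4 describes the Phase 2a dose as the largest that Phase 1 patients tolerated, and Table 1 limits the choice to groups A, B or C. On that reading no toxicity rate is claimed, and the empirical sample size is disclosed. This stands in part: the meaning is there, but it is loose, and it does not say what is reported when HIGH passes without a DLT.

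Second, Phase 2a adds 6 to 12 patients at the chosen dose, so 0/3 is not all the evidence by the final report. That is correct, and the pooled limits above show it. But no planned analysis combines the phases or feeds Phase 2a back into the MTD.

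Third, the SAP is not empty here. SAP 5.0 restates the safety criterion of no related Grade 3 or greater event, which is close to the DLT definition, and SAP 11.1 tabulates related events by treatment group and severity. Table shells and the DSMC Charter are separate documents that were not available, and a DLT listing may exist there. What can be said is that the SAP text plans no DLT summary and uses a different scale.

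A reader might go further than the documents allow:

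- **That HIGH was fixed by manufacturing alone.** Section 4.4 also names product stability, volume and vitreous scaling, and 3.6.3 adds conservative dog exposure and potentially efficacious doses. The figures are redacted, and no sentence equates HIGH with the feasible maximum.
- **That patients were told the dose is an MTD.** Consent pages were not available, so this cannot be checked.
- **That three patients per group without a power calculation is itself the defect.** That is ordinary in Phase 1.

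**Conclusion.** The objective as worded claims a property that the design does not have. The trial can describe which of three tested doses had an observed DLT. It cannot establish an MTD when no DLT occurs at HIGH, and it supports one only weakly when a DLT does occur. A cleared dose rests on about 0/3 at the Phase 2a decision (upper limit 70.8%). This could improve to 33.6% or 21.8% if the phases were pooled with no further DLT.

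The limits assume exactly three patients per Phase 1 group, which the protocol treats as a minimum, and Phase 2a at the same dose. The pass probabilities and the no-DLT scenarios rest on assumed rates and are illustrations.

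None of this shows that the Phase 2a dose is wrong or that the escalation rule should change. The fault lies in the stated objective and in the missing planned output.

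**What to change.** For reporting only:

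1. In protocol 3.9.2 and SAP 5.0, restate the objective as describing DLT occurrence at each of the three dose levels. State that the report will say the MTD was not reached if no DLT occurs at HIGH.
2. Add to SAP 11.1 a table of patients with a DLT (related event of CTCAE Grade 3 or higher, per protocol 7.4) by dose level, with count, n and exact 95% interval, shown by phase and pooled across phases at the same dose. Use the CTCAE grade that the stopping rule and the primary safety criterion already require. Keep the by-phase rows: in the 12-patient branch, half of Phase 2a has better acuity than the Phase 1 patients, so a pooled 0/15 mixes two populations. State the follow-up period counted.

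The sponsor and DSMC should also reconcile the uses of the MTD label (synopsis, 3.7, 3.15.1.2 with Table 1, 4.3, 4.4 and SAP 4.0) with the rules in 7.4. No dose, escalation rule or Phase 2a selection criterion is proposed here.

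The cost is wording, one table and a less ambitious objective. CTCAE grade must also be available in the analysis data, which the documents do not confirm. Protocol 11.3.6 finalises the analysis plan before the single database lock after Month 60, so the SAP change can be made if that lock has not taken place.
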